- Progressive disease should be confirmed on a second imaging study at least 4 weeks later and should demonstrate at least 10% or greater additional increase in disease burden. Alternatively, if the reviewing radiologist and the treating physician feel that there is unequivocal progression, then the patient may be eligible for crossover after discussion with the principal investigator.
- The patient has not experienced a nivolumab related adverse event(s) leading to permanent discontinuation.
- The patient should have completed at least one cycle of treatment before crossing over the combination treatment. It is not required that the patient receive all scheduled doses of nivolumab during this time; a minimum of 4 doses of nivolumab monotherapy must be given before crossover. Patients may crossover before 4 doses of nivolumab after discussion with the MSK principal investigator.
- The patient must have an ECOG of 0-1.
- In the opinion of the treating investigator, treatment with the combination of ipilimumab and nivolumab represents a reasonable treatment option for the patient.

For patients with bladder cancer, the combination treatment will be 3 mg/kg ipilimumab plus 1 mg/kg nivolumab. The first dose of the combination treatment will be administered at least 2 weeks, but no more than 6 weeks, after the most recent dose of nivolumab. The combination treatment will be administered once every 3 weeks for 4 doses and thereafter, patients will be treated with nivolumab every 2 weeks (240 mg) or every 4 weeks (480 mg) for up to 2 years, if the patient is clinically benefitting, the PI and treating investigator may elect to continue beyond two years.

Schema for Bladder Cancer (prior to Amendment 11)

Schema for Bladder Cancer (after Amendment 11)

See the study flowcharts (Section 10) for a depiction of study event scheduling.

Dosing Adjustments, Delays and Discontinuations

Dosing reductions/adjustments in response to toxicities of nivolumab or ipilimumab are not permitted. Patients who delay or discontinue treatment for toxicities should continue followup as per study calendar (i.e. imaging, study visits, laboratory followup).

Dose Delay Criteria/Criteria to Resume Treatment

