Patients who discontinue treatment early due to toxicity, should continue follow up with their study physician as clinically appropriate until the resolution or stabilization of the toxicity. Thereafter, they should continue to follow the study calendar until week 12 (i.e. study visits) and thereafter they should continue with tumor imaging (scans) q 6 months or every other scan, visits and labs.

If patients discontinue treatment due to toxicity after they have been on treatment for 12 weeks, then the q 12 week follow up will begin after the patient's end of treatment. If the patient did not have an end of treatment visit, the q 12 week follow up will begin after the patient's last dose. Patients who experience progression of disease after discontinuing

treatment early due to toxicity should move to survival follow-up. Patients in toxicity follow-up who initiate treatment with a new therapy will be immediately moved to survival follow-up.

For melanoma and bladder cancer patients receiving nivolumab or nivolumab plus ipilimumab, there is one follow up visit scheduled 6 weeks after the end of treatment. Additional follow up visits may be necessary at the discretion of the treating physician (i.e. for follow up of study related toxicities). All patients will be followed as per institutional guidelines in accordance with the usual standard of care principles.

Subjects who decline to return to the site for evaluations will be offered follow-up by phone every 3 months as an alternative. This will be documented in the patient's medical record.

As of MSK Amendment 21, all patients on active follow up should be taken off study as we prepare for study closure.

Survival Follow-up

Patients will be followed up by telephone (or by office visit) every 12 weeks (+/- 2 weeks) for 4 years from the start of treatment or until death. Follow-up calls or visits should begin 12 weeks (+/- 2 weeks) from the last study contact. Follow up calls must be documented in the patients' medical records.

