10.0 EVALUATION DURING TREATMENT/INTERVENTION

10.1 Standard Evaluation

Flowchart 1 - Nivolumab Monotherapy for Patients with Bladder Cancer

Study Section	Screening	Baseline	Initial Treatment							Treatment beyond Week 12 (up to 2 yrs) ^h (+/- 3 d)	End of Nivolumab Treatment ^e	
			0	2 (+/- 3 d)	4 (+/- 3 d)	6 (+/- 3 d)	8 (+/- 3 d)	10 (+/- 3 d)	12 (+/- 3 d)		If patient has not proceeded to Crossover Therapy	Last Day (EOT Only)
Study Week												
Study Day	-28 to -1	-14 to -1 (or as stated)	1	15	29	43	57	71	82			
Drug Administration												
Nivolumab (240 mg or 480 mg) ^a			X	X	X	X	X	X	x	q 2 wks (240 mg) OR q 4 wks (480 mg)		
Tumor Assessments												
Disease Staging	X											
Disease Assessment by RECIST 1.1 (including MRI or CT brain at screening)	X		Every 6 weeks (+/- 7 days) from first dose for the first 24 weeks and then every 12 weeks (+/- 7 days) thereafter until study discontinuation. ⁱ MRI or CT brain required at screening, but only necessary for subsequent disease assessments in patients with known disease metastatic to the CNS ^f									
Tumor Biopsy	X		2 weeks (- 5, +5 days) from first dose and before 2 nd dose of therapy ^g							At tumor progression (+ 14 days) ^g		
Other Examinations												
Eligibility Assessment and Informed Consent	X											
Demographics	X											
Medical History	X											
ECOG, Vital Signs (including Height, Weight), Physical Exam & collection of concomitant medications	X		X	X	X	X	X	X	X	q 2 weeks/ q 4 weeks ^j	X	X
EKG	X											
Adverse Events Assessment	X		X	X	X	X	X	X	X	q 2 weeks/4 weeks ^j	X	X
Labs & Assays												
Pregnancy Test (see Section 5.2.17, serum based) ^b		3mL									X	X
Urine pregnancy test (within 3 days prior to dosing) ^b			X	X	X	X	X	X	X	q 2 weeks/4 weeks ^j		
Chemistry (Comprehensive Metabolic Panel, LDH, TSH) ^c		X	X	X	X	X	X	X	X	q 2 weeks/4 weeks ^j	X	X
Blood Hematology (CBC with differential) ^c		X	X	X	X	X	X	X	X	q 2 weeks/4 weeks ^j	X	X
Research Blood Draw [mL] ^c	60mL		60mL	60mL	60mL	60mL	60mL	60mL	60mL		60 mL	
HIV, Hepatitis B and Hepatitis C	X											
Survival Follow-up ^d											X	X

- a. Nivolumab may be dosed no less than 11 days from the previous dose of drug.
- b. Pregnancy tests are not required if the patient is a male or a woman not of child-bearing potential
- c. Blood drawn prior to dosing drug. Blood must be drawn at all required timepoints. Results of thyroid functions tests are not required prior to dosing drug.

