12.0 CRITERIA FOR THERAPEUTIC RESPONSE/OUTCOME ASSESSMENT

Patients are considered evaluable for the primary and secondary endpoints if adequate sequencing data is generated from pre-study biopsy material to determine mutation burden/neo-antigen score.

Responses will be assessed by RECIST 1.1.

Additional clinical endpoints will be evaluated in an exploratory manner.

Duration of Response (DOR) Duration of Response will be determined for each patient with time origin at the first occurrence of confirmed response (CR,PR) until the first occurrence of confirmed progression or date of death if the patient dies due to any causes before progression. Every effort will be made to follow patients for progression after they discontinue the study.

Progression-free Survival (PFS) Progression-free Survival will be determined for each patient with time origin at the start of the treatment (day 1) until the first occurrence of confirmed progression or date of death if the patient dies due to any causes before progression. If a patient does not progress and is still alive, they will be censored on the date of last follow-up. Every effort will be made to follow patients for progression after they discontinue the study.

Overall Survival (OS) Overall survival (OS) will be measured for each patient with time origin at the start of the treatment (day 1) until recorded date of death. If a patient is still alive, they will be censored on the date of last follow-up. Every effort will be made to follow patients for overall survival after they discontinue the study.

Patient Evaluation & Statistics

All patients who receive at least one dose of nivolumab will be evaluated for tumor response (ORR, DOR), including patients who (1) develop rapid symptomatic disease progression, or (2) drop out early due to death or treatment-related toxicities. All patients who received at least one dose of nivolumab will be included in the clinical efficacy analyses of PFS and OS. Kaplan-Meier methodology will be implemented to estimate the median OS and PFS.

Of note, atypical responses are well known to occur in patients treated with immune checkpoint blockade, including early radiographic progression due to immune infiltration followed by subsequent radiographic response and durable clinical benefit. Thus, patients who

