Patients who receive at least 1 dose of nivolumab and have adequate biopsy material for whole exome sequencing and adequate sequencing data for determination of mutation burden will be considered evaluable for clinical and correlative objectives. Tumor mutation burden and neo-antigen score will be determined for each patient enrolled as described in section Appendix 3. We will perform the same analysis for patients according to their neo-antigen score (as described in Appendix 3). This analysis of the relationship between mutation burden and response rate will be performed for each tumor type independently.

It is anticipated that 4-5 patients per month will be accrued per cohort and accrual will be completed within two years.

Exploratory Endpoints

Patient Evaluation & Statistics for Clinical Endpoints

All patients who received at least one dose of nivolumab will be evaluated for clinical endpoints including tumor response (ORR, DOR, OS and PFS), rate of grade 3/4 toxicity, and survival. Patients who (1) develop rapid symptomatic disease progression, or (2) drop out early due to death will be treated as non responders. Patients who develop early toxicities that require treatment delay or discontinuation will continue to be evaluated for response on study. Kaplan-Meier methodology will be implemented to estimate the median survival time, median progression-free survival, and the PFS and OS rates. Overall survival will be defined as the time from treatment start to death or last follow-up; progression-free survival will be defined as the time from treatment start to the date of progression/death or last follow-up.

Exploratory Tumor and Peripheral Blood Immune Markers

The following endpoints will be evaluated in an exploratory fashion as sample availability permits. Descriptive statistics and graphical measures will be employed. Details related to methods are described in Appendix 3.

- 1. Compare tumor characteristic (mutation burden, neo-antigen score, PD-L1, TCR repertoire, immune infiltrate) between pre-treatment and on-treatment (optional) tumor biopsies**

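### PFS is censored at last follow-up, which can be a phone call without a scan, so PFS rates read slightly high

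*Combined protocol and SAP*

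**What the plan says.** **Censoring.** Section 12.0 says of PFS: "If a patient does not progress and is still alive, they will be censored on the date of last follow-up". Section 14.0 repeats it: "progression-free survival will be defined as the time from treatment start to the date of progression/death or last follow-up". Neither ties the date to a scan, and neither has a rule for missed scans or new anticancer therapy. For DOR, Section 12.0 gives a start and two end events but no censoring rule.

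**Contact without scans.** Section 4.2 creates two routes by which a patient without progression can be followed with no imaging:
- "Subjects who decline to return to the site for evaluations will be offered follow-up by phone every 3 months as an alternative".
- "Patients in toxicity follow-up who initiate treatment with a new therapy will be immediately moved to survival follow-up". Survival follow-up is then defined as: "Patients will be followed up by telephone (or by office visit) every 12 weeks (+/- 2 weeks) for 4 years".

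**Scan schedule after stopping for toxicity.** Flowchart 1 in Section 10.1 scans every 6 weeks to week 24, "then every 12 weeks (+/- 7 days) thereafter until study discontinuation". Footnote f of Flowcharts 1 and 2 and footnote g of Flowchart 3 hold patients who stop for toxicity to all protocol disease assessments and thin out only the other assessments. For those who stop early, Section 4.2 (Post-Treatment Follow-up) has them follow the calendar to week 12, and "thereafter they should continue with tumor imaging (scans) q 6 months or every other scan, visits and labs".

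**Status.** PFS and DOR are secondary objectives (Section 2.0). Sections 12.0 and 14.0 treat them as exploratory, with Kaplan-Meier estimates of PFS and no planned test.

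**The concern.** Overall survival needs only vital status, so a phone call is a sound censoring date for it. Progression under RECIST needs a scan. If a patient's last scan was at week 12 and the last phone call was at week 100, the plan's rule adds 88 weeks of progression-free time that nobody observed. Such patients stay in the risk set and can have an event only by dying. The error therefore has a known direction, upward, and a confidence interval does not allow for it. In a single-arm study the PFS and DOR estimates will be taken at face value, so the rule should be right even though nothing is tested on them.

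**Working it through.** The plan gives no PFS assumption or precision figure, so there is nothing of its own to reproduce. The calculation below is illustrative.

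**Inputs**
- From the documents: scans at weeks 6, 12, 18, 24, 36, 48 and so on; 71 bladder patients (Section 14.0); death counts as a PFS event.
- Assumed: exponential time to progression with median 26 weeks, so a = ln 2/26 = 0.0267 per week; death only after progression, with post-progression median m = 13, 26 or 52 weeks and b = ln 2/m; 10% of patients phone-only after week 12; progression found outside the study ignored, which makes the results upper bounds.

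**Step 1. Upper bound if no phone-only patient dies.** With S(t) = exp(−at), S(12) = 0.726 and S(48) = 0.278. Week-52 PFS is 0.9 × 0.278 + 0.1 × 0.726 = 0.323 against 0.278, a shift of 4.5 points.

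**Step 2. Deaths counted.** Let G(s,t) be the probability of progressing after week s and being alive at week t:

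G(s,t) = e^(−at) + ∫ₛᵗ a e^(−au) e^(−b(t−u)) du.

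At week 52 a scanned patient is event-free with probability G(48,52), and a phone-only patient with probability G(12,52). The shift is 0.1 × [G(12,52) − G(48,52)].

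| m (weeks) | G(12,52) | G(48,52) | Shift, week 52 |
|---|---|---|---|
| 13 | 0.414 | 0.275 | +1.4 points |
| 26 | 0.517 | 0.277 | +2.4 points |
| 52 | 0.602 | 0.277 | +3.2 points |

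At week 104 the same formula, with week 96 as the last scan, gives +0.5 to +2.9 points. A 5% share halves every figure. The median stays at week 36, except with m = 13, where it moves from 33.8 to 35.3 weeks.

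**Step 3. Cross-check under other assumptions.** A Kaplan-Meier simulation used a true median of 3 or 6 months, 10% phone-only from a point between 1.5 and 12 months, and a median of 10 months from progression to death. It compared censoring at last contact with censoring at last scan. Twelve-month PFS was 9.5% against 7.8%, and 29.5% against 27.4%: shifts of 1.7 and 2.1 points. The medians did not move.

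**Step 4. Scale.** The 95% half-width at PFS 0.28 with 71 patients is 1.96 × √(0.28 × 0.72/71) = 0.104, or 10 points.

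**Step 5. Does the fix work?** Simulated trials of 71 patients (follow-up 26 to 208 weeks, 10% phone-only, phone-only status independent of prognosis, m as above) gave these week-52 PFS values:

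| Rule | Week-52 PFS |
|---|---|
| Everyone scanned | 27.6–27.8% |
| Plan's rule | 29.1–31.1% |
| Last-scan censoring, all deaths as events | 28.1–29.1% |
| Same, deaths after two missed scans censored | 27.3–27.7% |

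**Step 6. Scan-schedule conflict.** Suppose 10% stopped for toxicity before week 12 and were then scanned at weeks 36, 60 and so on. Week-26 PFS would be 0.9 × S(24) + 0.1 × S(12) = 0.547 against 0.527 (+2.0 points), and week-52 PFS 0.9 × S(48) + 0.1 × S(36) = 0.289 against 0.278 (+1.0). Averaged over weeks 12 to 103, the shift across the possible schedules is 0.1 to 0.6 points. This delay in detection arises under either censoring rule.

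**The case against.** **Last follow-up may mean follow-up for progression.** Section 12.0 follows the PFS censoring sentence with a promise of best efforts to keep following patients for progression, whereas the OS paragraph refers to survival. That is a fair reading of intent. It does not set a censoring date, and Section 14.0 repeats the rule without it. An analyst could defensibly use the last phone call.

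**Few patients are affected.** This largely stands. Most patients in telephone survival follow-up have already progressed and had their PFS event. Those left are patients who decline visits or who start new therapy in toxicity follow-up, and the documents do not say how many there are.

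**The size is small.** This stands. The shift is well inside sampling error on a descriptive secondary endpoint.

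**The test of the fix assumes its own answer.** This stands in part. The simulation makes leaving scans independent of prognosis, which is the condition under which last-scan censoring is unbiased. Hence the sensitivity analyses.

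**A stronger reading of the schedule conflict.** A reader might infer that everyone off drug for toxicity goes to six-monthly scans. The text does not support that: the sentence concerns early stoppers who follow the calendar to week 12, and the next paragraph of Section 4.2 gives later stoppers a separate 12-week follow-up. Nor does the 17.0% grade 3–4 event rate in Section 3.0 measure early discontinuation, so the 10% in Step 6 has no basis in the documents.

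**Conclusion.** The concern holds in a limited form. The stated rule, followed literally, counts unscanned time as progression-free and biases PFS rates upward by about 1 to 3 points at week 52 if 10% of patients are phone-only. That rests on the assumed share, exponential progression with a 26-week median, and no progression found outside the study. The median is mostly unchanged. A reader might infer that the PFS results are unreliable or that the response-rate or AUC analyses are touched; neither follows, since the shift is small beside a 10-point half-width and neither primary analysis uses PFS. The scan-schedule conflict is real but secondary. It affects only patients who stop for toxicity before week 12, changing the censoring date does not cure it, and it matters little now that Amendment 21 takes patients in active follow-up off study.

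**What to change.** In Sections 12.0 and 14.0:
- Censor PFS and DOR at the last adequate tumour assessment for patients alive without documented progression.
- Keep death from any cause as an event in the main analysis, as the plan already defines it. Step 5 shows this leaves a residual of roughly 0.5 to 1.3 points (28.1 − 27.6 and 29.1 − 27.8).
- Add a sensitivity analysis that censors, at the last adequate scan, patients whose death follows two or more missed scans. This is better as a sensitivity analysis than as the main rule, because it departs from the plan's event definition and may itself censor informatively.
- Add a second sensitivity analysis that treats progression as interval-censored between the last progression-free scan and the first scan showing progression.
- Report how many patients were followed by phone only.

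In Section 4.2, make the sentence on scans after early toxicity discontinuation follow the flowchart schedule.

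The cost is one censoring rule, two sensitivity analyses on scan dates already recorded and one corrected sentence, with no new visits. PFS may come out slightly lower. Last-scan censoring assumes that leaving scans is unrelated to prognosis, and the report should say so.

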5.0 THERAPEUTIC/DIAGNOSTIC AGENTS

PRODUCT INFORMATION TABLE: Please also see Pharmacy manual in Appendix 1.

Product Description and Dosage Form	Potency	Primary Packaging (Volume)/Label Type	Secondary Packaging (Qty) /Label Type	Appearance	Storage Conditions (per label)
Nivolumab BMS-936558-01 Solution for Injection	100 mg (10 mg/mL)	10 mL vial	5-10 vials per carton/ Open-label	Clear to opalescent colorless to pale yellow liquid. May contain particles	Protect from light and freezing
Ipilimumab Solution for Injection	200 mg (5 mg/mL)	40 mL vial	4 vials per carton/Open-label	Clear, colorless to pale yellow liquid. May contain particles	2 to 8°C. Protect from light and freezing.

*Nivolumab may be labeled as BMS-936558-01 Solution for Injection

If stored in a glass front refrigerator, vials should be stored in the carton. Recommended safety measures for preparation and handling of nivolumab and ipilimumab include laboratory coats and gloves.

For additional details on prepared drug storage and use time of nivolumab or ipilimumab under room temperature/light and refrigeration, please refer section 8.8 and to the BMS-936558 (nivolumab) and Ipilimumab Investigator Brochure section for "Recommended Storage and Use

Conditions"

Estimated Requirements for Study Drug:

Drug	Source	Required Quantity
--------------------	----------------------	---------------------------------

For melanoma cohort:

Nivolumab	BMS	Up to 667,200 mg Induction - 19,200 mg (60 pt x 80 kg x 1 mg/kg x 4 doses) Maintenance – 648,000 mg (60 pt x 80 kg x 3 mg/kg x 45 doses)
Ipilimumab	BMS	Up to 57,600 mg (60 pt x 80 kg x 3 mg/kg x 4 doses)

For bladder cohort:

Nivolumab	BMS	Up to 705,600 mg Induction – 57,600 mg (60 pt x 80 kg x 3 mg/kg x 4 doses) Maintenance/ Monotherapy – 648,000 mg (60 pt x 80 kg x 3 mg/kg x 45 doses)
Ipilimumab	BMS	Up to 19,200 mg (60 pt x 80 kg x 1 mg/kg x 4 doses)

Drug Dosing

For patients receiving nivolumab monotherapy, the drug shall be dosed at a dose of 240 mg (every 2 weeks) or 480 mg (every 4 weeks).

For patients initiated on treatment, or initiated on crossover treatment after the approval of Amendment 11, the dosing for the combination of ipilimumab and nivolumab will be ipilimumab 3 mg/kg and nivolumab 1 mg/kg for both bladder and melanoma patients. For patients who initiated treatment with the combination of ipilimumab and nivolumab prior to Amendment 11, they will maintain their current dosing/schedule.

For patients receiving the combination of nivolumab and ipilimumab, the dosing calculations should be based on the actual body weight at screening (within 28 days of starting therapy). For Bladder crossover patients, the baseline weight for crossover should be used for dosing calculations instead of the weight collected during screening for monotherapy. For all patients receiving the combination of nivolumab and ipilimumab, if the subject's weight within 5 days of dosing differs by > 10% from the weight used to calculate the original dose, the dose must be recalculated. All subsequent dosing should use the baseline weight unless the patients weight has changed by > 10% from the weight used to calculate the original dose. If the patients dose differs by > 10% from the weight used to calculate the original dose, the dose must be recalculated. All doses should be rounded to the nearest milligram. There will be no dose modifications allowed. See appendix 1 for additional details.

Drug Storage, Preparation and Administration

See appendix 1.

Ipilimumab and Nivolumab will both be provided by BMS to the study sites. An IND for each agent will be cross filed and will be held by MSKCC, the data coordinating center.

